18F-FDG-PET=[¹⁸F]Fluorodeoxyglucose, 3QM=Every 3 months, AESI=adverse events of special interest, CT=computed tomography, ECOG PS=Eastern Cooperative Oncology Group Performance Status, EOS=End of Study, EOT=End of Treatment, FU=Follow-up, MRI=magnetic resonance imaging, PD=progressive disease, SAE=serious adverse event

Figure 3 Treatment Diagram and Time Window for Visits

C=cycle, D=day, EOT=end of treatment, IMRT=intensity-modulated radiation therapy, QW= once a week, W=week.

- On days when IMRT is to be administered, xevinapant must be administered before IMRT.
- During the treatment period, each study visit day and allowed time windows will be based on the C1D1 date. C1D1 and C1D2 are triggered by the first administration of xevinapant and QW cisplatin, respectively. These visits should be performed on consecutive days. Crossed gray boxes in the row "Time Window for Visit" represent days around a specific study visit (represented by solid black boxes in the row "Study visit day") where the visit can be rescheduled (see also time windows planned in the SoA, [Table 1](#), [Table 2](#), and, [Table 3](#)).
- Xevinapant once daily from D1 to D14 of each cycle (solid red boxes) [CCI](#)
- Cisplatin-based chemotherapy weekly on C1D2, C1D9, C1D16, C2D2, C2D9, C2D16, and C3D2 (see also Section [6.5.2](#)). For participants not eligible to continue with QW cisplatin after dose reduction switch to carboplatin at the next scheduled chemotherapy administration.
- IMRT should be delivered in 35 fractions over 7 weeks, 5 fractions weekly (solid yellow boxes). If IMRT is put on hold due to safety or administrative reason, the 7 weeks of IMRT can be administered until Study Week 9 (dotted yellow boxes) (also see Section [6.5.3](#)).
- The EOT visit will be performed 14 days (\pm 7 days) after last study intervention administration (i.e. xevinapant, chemotherapy, or IMRT whichever is administered last) or 14 days (\pm 7 days) after premature discontinuation during treatment, but prior to start of any subsequent anticancer therapy.

Table 4

Schedule of Activities: Pharmacokinetic Assessments

Treatment Day	Timepoint	Xevinapant PK Sampling
C1D2	Predose xevinapant (window: less than 1 hour prior to dosing)	X
C1D2	End of cisplatin infusion (window: less than 30 min after end of infusion)	X
C1D9	Predose xevinapant (window: less than 1 hour prior to dosing)	X
C1D9	1-2 hours after end of cisplatin infusion	X

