6.5.2.2 End of Chemotherapy

Chemotherapy will be administered until completion of the 7 weekly infusions of platinum-based therapy planned in the study or until any of the study intervention discontinuation criteria described in Section 7.1 occur.

Note: Chemotherapy discontinuation will **not** automatically have to result in xevinapant discontinuation or IMRT discontinuation

Dose modifications, treatment interruption, switching from cisplatin to carboplatin, and permanent discontinuation of any of the components of the study intervention is to be recorded in the Dosing CRF of each component of the study intervention. For each action, the reason must be recorded.

Discontinuation from study intervention does not mean discontinuation from the study. Procedures to be followed in the event of a study intervention discontinuation are presented in Section 7.1.

Procedures for discontinuation from study (not only study intervention) are described in Section 7.2.

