6.5.3.2 Treatment

Full details of radiotherapy protocol requirements including volumes, OAR, and OAR dose constraints can be found in the RT Manual provided for this study. A QA procedure will be applied for this study. The RT-QA Review Center (Appendix 5) will centrally review the IMRT treatment plan(s) including other treatment-related information submitted by the Investigator to ensure compliance with protocol guidelines and provide feedback to the site (refer to the RT Manual). The IMRT plan must be reviewed by the RT-QA Review Center prior to the start of the IMRT. A summary of radiotherapy requirements and recommendations is described below.

CCI

A matched conventional anterior neck field is not permitted. During treatment, daily image-guided radiation therapy (IGRT) is required with either kV or MV guidance.

For CT simulation, the participant must be in a supine position and immobilized with a thermoplastic (or similar) mask that includes the head and neck with strong consideration of the shoulders as well. Intraoral immobilization devices are at the discretion of the Investigator. A slice thickness of 3 mm or less is required and the field of view must extend from the top of skull to the bottom of the carina. Intravenous contrast is recommended at the time of simulation.

Standard fractionation IMRT (as fully described in the IMRT manual) is to be started on C1D1 after administration of xevinapant (see administration schedule in [Table 2](#)). On days where all treatment components should be administered, IMRT should be preferably administered after xevinapant and chemotherapy.

IMRT will be delivered per [Table 9](#) and the following:

- To the PTV and high-risk clinical target volume: 70 Gy in 35 fractions over 7 weeks, 2.0 Gy/fraction, 5 days/week. Missed treatments due to holidays or logistic reasons can be compensated by delivering the missed fraction before or after the end of the combination treatment period (i.e. up to Week 9 after administration of first dose) (see Section [6.5.3.3](#)).
- Elective irradiation (low risk) to locoregional areas, 56 Gy (1.6 Gy/fraction per day, 5 fractions per week [5/7 days]).

Table 9 **Radiation Therapy Scheme**

	Total dose in Gy	Dose in Gy	Number of days	
PTV 70	70	2	35	5 fractions per week over 7 weeks
PTV 56	56	1.6	35	5 fractions per week over 7 weeks

PTV=Planning target volume.

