## 13 Study Intervention: Compliance and Exposure

The following analyses will be performed based on SAF.

All dosing calculations and summaries will be based on “Study Drug Administration” CRFs pages.

If the total dose is missing, the protocol defined dose of each study intervention will be used.

No imputation of missing start dates of study interventions will be done.

In case the last date of study intervention is incomplete the date of last study intervention administration will be taken from the End of Treatment page.

For Cycle X, actual cycle start date for each participant is:

- the earliest start date of dosing in the Cycle X Day 1 visit eCRF exposure page, if the participant received any study intervention on that visit (i.e., any study intervention with dose>0 at that visit)
- the first day of assessments in the Cycle X Day 1 visit, if the participant did not receive study intervention on that visit (i.e., all study interventions had dose=0 at that visit). Use start date in the exposure page if available; if start date is not available then use date of collection of vital signs (assuming vital signs are the first assessment of the cycle on Cycle X Day 1 visit).

Actual cycle end date for each participant is:

- for all cycles X except the last cycle, actual cycle end date = actual cycle (X+1) start date – 1 day;
- for the last cycle, actual cycle end date = actual cycle start date + intended cycle duration (in days) – 1 day

Cycle duration (weeks) = (actual cycle end date – actual cycle start date + 1)/7

When summarizing exposure for each study intervention, only cycles with non-zero dose of study intervention of at least one of the study interventions should be included.

A dose is regarded to be administered, if the actual dose received is > 0, or the duration of the infusion is > 0, or the start date or end date is not missing.

**Xevinapant Cumulative dose (mg)** overall is the sum of the actual doses of study intervention received overall. Actual dose per day is collected using mL on eCRF. This dose will be converted to mg as:

$$\text{Actual dose (mg)} = \text{Actual dose (mL)} * 20 \text{ (mg/mL)}$$

**Xevinapant Dose intensity (mg/day)** is defined as the cumulative dose of xevinapant by the cycle duration in days as:

$$\text{dose intensity} = \left( \frac{\text{cumulative dose}}{(\text{planned dosing days per cycle (14 days)}) * \text{exposure duration (cycles)}} \right)$$

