**Cisplatin/carboplatin Cumulative dose (mg/m^2 or AUC)** overall is the sum of the actual doses of study intervention received overall, respectively.

**Cisplatin/carboplatin Dose intensity (mg/m^2/day or AUC/day)** is defined as the cumulative dose of cisplatin/carboplatin by the exposure duration in days as:

$$\text{dose intensity} = \left( \frac{\text{cumulative dose}}{(\text{planned dosing days per week (1 day)}) * \text{exposure duration (weeks)}} \right)$$

**IMRT Cumulative dose (Gy)** overall is the sum of the actual doses of study intervention received overall. If a IMRT dose modification will occur PTV1 new reported value will be used for the calculation.

**IMRT Dose intensity (Gy/day)** is defined as the cumulative dose of IMRT by the exposure duration in days as:

$$\text{dose intensity} = \left( \frac{\text{cumulative dose}}{(\text{planned dosing days per week (5 days)}) * \text{exposure duration (weeks)}} \right)$$

**Relative dose intensity (%)** is defined as the actual dose intensity divided by the planned dose intensity during the study and expressed in percentage:

$$\text{relative dose intensity} = \left( \frac{\text{dose intensity}}{\text{planned dose}} \right) * 100$$

Where the planned dose is:

- Xevinapant: **CCI** mg/day
- Cisplatin: **cci** mg/m^2/day
- Carboplatin: AUC2/day
- IMRT: 70 Gy/day

The summary of study intervention exposure will include the following information:

- Total duration of xevinapant, cisplatin, carboplatin and IMRT (weeks) and by categories of  $\leq$  3 weeks,  $> 3 - 6$  weeks,  $> 6 - 9$  weeks,  $> 9 - 12$  weeks,  $> 12 - 15$  weeks,  $> 15 - 18$  weeks
- Number of IMRT Fractions
- Total number of cycles received of xevinapant, cisplatin, carboplatin and IMRT
- Cumulative dose of xevinapant, cisplatin, carboplatin and IMRT
- Dose intensity of xevinapant, cisplatin, carboplatin and IMRT
- Relative dose intensity (%) of xevinapant, cisplatin, carboplatin and IMRT
- Dose reduction of xevinapant, cisplatin, carboplatin and IMRT per time period (overall and by reason)
- Missed doses of xevinapant, cisplatin, carboplatin and IMRT per time period
- Discontinuation of xevinapant, cisplatin, carboplatin and IMRT per time period (overall and by reason)
- A listing will be provided for all administrations of participants for the primary analysis only.

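### SAP Section 13 sets platinum and IMRT dose against dosing in every exposure week although only 7 weeks are planned, and its IMRT planned dose of 70 Gy per day conflicts with the protocol's 2 Gy per fraction

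*SAP*

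**What the plan says.** SAP Section 13 defines dose intensity for cisplatin and carboplatin as cumulative dose divided by the product of "planned dosing days per week (1 day" and exposure duration in weeks. For IMRT the first factor is "planned dosing days per week (5 days". Relative dose intensity then divides by a listed planned dose: redacted for cisplatin, "Carboplatin: AUC2/day" for carboplatin, and 70 Gy per day for IMRT.

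The one visible definition of a duration in weeks in that section is "Cycle duration (weeks) = (actual cycle end date – actual cycle start date + 1)/7". The last cycle is run to its full intended length. For each intervention's exposure summary, a cycle counts if any one of the interventions had a dose above zero in it. SAP Section 9.9 is titled for exposure time, but its text is redacted.

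The protocol plans less platinum and IMRT than those denominators imply:

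- Protocol 6.5.2.2 ends chemotherapy at "completion of the 7 weekly infusions of platinum-based therapy planned in the study".
- The notes to the treatment diagram in Protocol 1.3 give the days: "Cisplatin-based chemotherapy weekly on C1D2, C1D9, C1D16, C2D2, C2D9, C2D16, and C3D2".
- Protocol 6.5.3.2 gives IMRT as "70 Gy in 35 fractions over 7 weeks, 2.0 Gy/fraction, 5 days/week".
- The synopsis gives 18 weeks of treatment in six 3-week cycles. The last three cycles are xevinapant alone.

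**The concern.** The formulas treat every exposure week as a planned dosing week. That suits xevinapant, which is planned in all six cycles. It does not suit components planned for 7 weeks. The combination period is 9 weeks long, and Cycles 4 to 6 stay in the platinum and IMRT summaries under the visible rule because xevinapant is given in them. If weeks are built from those cycles, weeks with no planned dose count as missed dosing. A participant who stays longer on xevinapant then gets a lower cisplatin figure for identical chemoradiation.

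IMRT has a second problem. Its planned daily dose is listed as the number that the protocol gives for the whole course.

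Dose intensity and relative dose intensity remain in the reduced output list for the synoptic report (SAP 7.1). Whether adding xevinapant impairs delivery of chemoradiation is a natural question for this output: Protocol 2.2 makes a statement on it for the three-weekly cisplatin regimen. A table in which complete delivery does not read as 100% answers that question badly.

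**Working it through.** **Inputs**

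- Planned infusions: 7, on study days 2 to 44 (Protocol 1.3, 6.5.2.2).
- Planned IMRT: 35 fractions of 2 Gy. 35 × 2 = 70 Gy and 35/5 = 7 weeks, so the protocol's own figures agree (Protocol 6.5.3.2).
- Candidate exposure weeks, W: 3 cycles × 3 = 9; 6 cycles × 3 = 18; first to last infusion plus a 7-day interval, (44 − 2 + 7)/7 = 7; bare first-to-last span, (44 − 2 + 1)/7 = 6.14.
- Carboplatin: Protocol 6.5.2 asks for at least one full cisplatin infusion before a switch, which leaves at most 6.

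The documents state no relative dose intensity, so there is no plan figure to reproduce. I assume full delivery on schedule at the planned dose per m².

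**Cisplatin.** With planned dose D, dose intensity = 7D/(1 × W). Dividing by D gives relative dose intensity = 7/W, so the redacted dose cancels.

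**Carboplatin, six infusions.** Relative dose intensity = 6/W on cycle-based weeks.

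**IMRT.** Dose intensity = 70/(5 × W), then divided by the listed 70 Gy per day. The last column divides by 2 Gy instead, to separate the effect of the weeks from the effect of the listed dose.

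| W | Cisplatin | Carboplatin (max. 6) | IMRT intensity, Gy/day | IMRT ÷ 70 | IMRT ÷ 2 |
|---|---|---|---|---|---|
| 9 (three cycles) | 77.8% | 66.7% | 1.556 | 2.2% | 77.8% |
| 18 (six cycles) | 38.9% | 33.3% | 0.778 | 1.1% | 38.9% |
| 7 | 100% | – | 2.0 | 2.9% | 100% |
| 6.14 (bare span, Days 2–44) | 114% | – | – | – | – |

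Carboplatin on its own span plus 7 days: (44 − 9 + 7)/7 = 6 weeks, so 6/6 = 100%.

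**Size of the week effect.** 9/7 = 1.29 and 18/7 = 2.57, so a cycle-based denominator is 29% or 157% too large for a 7-week component.

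**Size of the IMRT entry.** Reaching 100% against 70 Gy per day needs 70/(5 × W) = 70, so W = 0.2 weeks. None of the durations above comes near that.

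**Contrast.** Xevinapant, in planned daily doses: 84/(14 × 6) = 100%. The structure works for the component planned in every cycle.

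**The case against.** The strongest objection is that cycle-based weeks are inferred. No visible sentence says that exposure duration in weeks is the sum of cycle durations, and the section that would settle it is redacted. Redacted text is not missing text. The visible wording even leans the other way in places. For xevinapant the SAP speaks of cycle duration and divides by cycles. For platinum and IMRT it speaks of exposure duration and divides by weeks. It also lists a total duration in weeks for each component, which would be pointless if all components shared the same cycles. A per-drug span with the 7-day interval added returns exactly 100% for cisplatin. All of this stands, and it is why the 77.8% and 38.9% are conditional.

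It does not remove the point. The cycle-inclusion rule is visible, is stated for each intervention, and does not fit components planned for 7 weeks. A per-drug span also needs an explicit convention: without the added interval cisplatin reads 114%. The same convention does not carry over to IMRT. Assuming a Monday start and no missed fraction (Days 1 to 47), last dose plus 7 days is 53/7 = 7.57 weeks, or about 92% against 2 Gy. The bare span is 47/7 = 6.71 weeks, or about 104%. The 70 Gy per day entry is visible and owes nothing to the redaction.

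A reader might infer that the SAP as written will report 78% or 39% for all three components. The documents do not support that. IMRT is divided by 70 Gy per day and comes out near 1% to 3%, carboplatin cannot reach 7 infusions, and the cisplatin figures rest on a definition that cannot be seen.

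The impact is also limited. The study has one arm, and relative dose intensity is descriptive. The DLT-like rules use the percentage of planned cumulative dose. SAP Section 13 also specifies cumulative dose, number of fractions, dose reductions, missed doses and discontinuations.

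**Conclusion.** The point holds in conditional form for platinum and on visible text for IMRT.

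- **Cisplatin:** if exposure weeks are cycle-based, full delivery reads 77.8% (9 weeks) or 38.9% (18 weeks). Under a per-drug span it reads 100% or 114%, depending on whether the last 7-day interval is added.
- **Carboplatin:** the cycle-based ceilings are 67% and 33%, provided the one-infusion condition before switching is followed.
- **IMRT:** full delivery reads 2.2%, 1.1% or 2.9% at 9, 18 or 7 weeks, because the SAP's planned dose per day and the protocol's dose per fraction disagree. These passages must be reconciled.

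Severity is minor. A reader might infer that the tolerability conclusion is at risk. It is not: no endpoint, stopping rule or analysis-set rule uses dose intensity. What is at risk is a misleading exposure table in the synoptic report.

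**What to change.** In SAP Section 13:

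- Make the cycle-inclusion rule component-specific, so that Cycles 4 to 6 do not enter the platinum and IMRT summaries because of xevinapant alone.
- Base platinum and IMRT relative dose intensity on that component's scheduled administrations: 7 infusions and 35 fractions, and for carboplatin the infusions remaining after the switch. State or cross-reference each component's exposure duration wherever weeks are still used.
- Reconcile the IMRT planned-dose entry with the per-fraction dose in Protocol 6.5.3.2.
- Report the percentage of the full planned cumulative dose alongside. If the denominator is cut off at discontinuation, a participant who stops cisplatin after two full infusions scores 2/2 = 100%. Against the full plan the figure is 2/7 = 28.6%, so early stopping stays visible.

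The cost is SAP wording and a programming change. No new data are needed.

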# 7 Changes to the Planned Analyses in the Clinical Study Protocol

## 7.1 Overview of Planned Analyses after discontinuation of Xevinapant trials

A review of the TrilynX study (MS202359\_0006) data suggests that the experimental arms with Xevinapant demonstrated either lower efficacy compared to the control group or limited potential for added benefit over standard of care.

Consequently, the scope of analyses for this study (MS202359\_0025) has been reduced. The analyses outlined in Section 6 will not be conducted as originally planned. However, following analyses will be performed instead:

- an analysis for the first SMC with 6 patients,

- an analysis using the primary analysis DBL date of 20-SEP-2024 for a synoptic CSR.

The analyses considered relevant for a synoptic CSR are listed below:

- Study Subject Data:
  - Participant disposition
    - Subject Disposition Status
    - Analysis Sets
  - Enrollment details
  - Demographic Characteristics
  - Medical History
  - Other Baseline characteristics
    - Disease History
  - Previous and Concomitant Medications, Procedures, Follow-up Treatments
    - Previous Medication
    - Concomitant Medication
    - Concurrent Procedures
  - Treatment Compliance and Exposure
    - Duration of Therapy
    - Cumulative Dose, Dose Intensity, Relative Dose Intensity
    - Dose Reductions
    - Therapy Delays
- Safety Data:
  - Display of Adverse Events
    - Overview of Treatment Emergent Adverse Events (TEAEs)
    - Overview of TEAEs Leading to Discontinuation / Dose Reduction of Treatment
    - TEAEs by Primary System Organ Class (SOC) and Preferred Term (PT)
    - Study Intervention Related TEAEs by SOC and PT
    - Serious TEAEs by SOC and PT
    - Non-serious TEAEs by SOC and PT at a Frequency Threshold of 5%
    - TEAEs by Worst Grade, SOC and PT
    - Study Intervention Related TEAEs by Worst Grade, SOC and PT
  - Deaths, Other Serious and Significant Adverse Events

- Deaths by Primary Reason
- Listing of Deaths
- Listing of Serious TEAEs
- Clinical Laboratory Evaluations
  - Hematology - Summary Statistics over Time
  - Hematology - Shift in Toxicity Grading from Baseline to Highest Grade
  - Biochemistry - Summary Statistics over Time
  - Biochemistry - Shift in Toxicity Grading from Baseline to Highest Grade
- Other Safety Evaluations
  - Vital Signs Results Summary Statistics Over Time
  - ECG Results - Summary Statistics Over Time
- Subject Data Listings:
  - Discontinued Subjects

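### SAP Section 13 divides IMRT dose intensity by the 70 Gy course total labelled as a daily dose, so IMRT relative dose intensity comes out 35 times too small

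*SAP*

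**What the plan says.** SAP Section 13 defines relative dose intensity in words: it "is defined as the actual dose intensity divided by the planned dose intensity during the study and expressed in percentage". The formula beneath divides dose intensity by a listed planned dose. For IMRT that list gives 70 Gy/day.

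The same section says that IMRT dose intensity, in Gy/day, "is defined as the cumulative dose of IMRT by the exposure duration in days". The printed formula is cumulative dose divided by 5 planned dosing days per week times exposure duration in weeks.

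Protocol Section 6.5.3.2 sets the prescription for the high-risk volume as "70 Gy in 35 fractions over 7 weeks, 2.0 Gy/fraction, 5 days/week". Table 9 and the overall design in Section 4.1 agree.

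SAP Section 7.1, which cuts the analyses down to a synoptic report, retains "Cumulative Dose, Dose Intensity, Relative Dose Intensity" under treatment compliance and exposure.

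**The concern.** The sentence asks for planned dose intensity, a rate. The number supplied for IMRT is the dose of the whole radiotherapy course with a per-day unit attached. Because numerator and denominator both carry the label Gy/day, the mismatch does not show in the units.

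A programmer who follows the formula and the list would report an IMRT relative dose intensity of about 3% for participants who completed radiotherapy on time. Radiotherapy is one of the three components of the combination, and exposure is among the few results still planned for the report.

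**Working it through.** **Inputs**
- IMRT numerator: cumulative Gy / (5 × exposure weeks) (SAP Section 13, printed formula).
- Listed IMRT planned dose: 70 Gy/day (SAP Section 13).
- Prescription: 70 Gy, 35 fractions, 2 Gy per fraction, 5 per week, 7 weeks (protocol Section 6.5.3.2 and Table 9).

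**Step 1: can 70 Gy/day be reproduced?** Planned dose intensity on the SAP's scale is 70 / (5 × 7) = 2 Gy/day. The figure 70 arises only as the course total, 35 × 2 Gy. The lower-dose volume does not explain it either: 56 / 35 = 1.6 Gy/day.

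**Step 2: size of the error.**
- As written: [Gy / (5 × weeks)] / 70 × 100.
- With planned intensity: [Gy / (5 × weeks)] / 2 × 100.
- Ratio of the two: 70 / 2 = 35. Dose received and duration cancel, so the factor is constant.

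**Step 3: examples.** The percentages depend on how exposure duration is counted. The SAP's definition of exposure time (Section 9.9) is not visible in the public version, so the durations below are assumptions.

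| Dose and duration | Dose intensity (Gy/day) | As written | With 2 Gy/day |
|---|---|---|---|
| 70 Gy, 47 days (6.714 weeks) | 2.085 | 2.98% | 104.3% |
| 70 Gy, 7 weeks | 2.000 | 2.86% | 100% |
| 70 Gy, 8 weeks | 1.750 | 2.50% | 87.5% |
| 70 Gy, 9 weeks | 1.556 | 2.22% | 77.8% |
| 50 Gy, 7 weeks | 1.429 | 2.04% | 71.4% |

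The 47-day row counts from first to last fraction for an uninterrupted course starting on a Monday (6 × 7 + 5 = 47). A midweek start lengthens it; a Wednesday start ends on day 49, which is the 7-week row. The 9-week row is the upper end, because the notes to protocol Figure 3 say that after a hold "the 7 weeks of IMRT can be administered until Study Week 9".

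**Step 4: the other entries in the list.** Carboplatin is listed as AUC 2 per day, with a numerator of cumulative AUC / (1 × weeks). Six weekly doses of AUC 2 give 12 / 6 = 2, and 2 / 2 = 100%, so that line is consistent. The xevinapant and cisplatin values are redacted; only their per-day units can be seen, and these fit their formulas.

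**Step 5: where the value is used.**
- The DLT-like criteria (protocol Section 8.2.5.1, SAP Section 15.1) use a radiotherapy delay of more than 2 weeks, not IMRT relative dose intensity.
- The 60% cumulative-dose rule for the DLT set (protocol Table 16) covers xevinapant and cisplatin only.
- The sample size (protocol Section 9.2) does not use it.
- IMRT cumulative dose, number of fractions, duration, dose intensity, missed doses and discontinuations are summarised separately and do not use the constant.

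**The case against.** The strongest objection is about weight. No hypothesis is tested, the efficacy analyses have been dropped, and no decision rule uses this statistic. A value near 3% beside a cumulative dose of 70 Gy and 35 fractions would look wrong at once. All of that stands, and it keeps the point minor.

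A second objection is that the SAP contains two rules. The sentence is right and only the formula with its list is wrong, so a programmer who followed the sentence would get the correct result. That is also fair: the output may already be right. But the text then contradicts itself, and a correct table would depart from the listed constant with nothing to document why.

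Third, Section 7.1 retains relative dose intensity without naming the interventions, so an IMRT row in the synoptic report is an inference. It is a reasonable one, because Section 13 names IMRT explicitly in its list of relative dose intensity summaries. The same value could also appear in the compliance and exposure listing that Section 7.1 keeps.

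Fourth, the modification history dates version 1.0 to 22 April 2024 and records Section 7.1 as the only change in version 2.0. On that record the IMRT line was written before the database lock and carried forward. The log may be incomplete, since Sections 14 and 16 also refer to Section 7.1. None of these points alters the constant.

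**Conclusion.** The concern holds. The IMRT planned dose of 70 Gy/day is a course total with a per-day label and does not match the SAP's own definition. Used as written, it makes every IMRT relative dose intensity 35 times too small; a full course in 7 weeks shows 2.86% instead of 100%.

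The factor of 35 rests on the printed numerator formula and the protocol prescription. It does not depend on the missing exposure-time definition; only the example percentages do. Whether any output is wrong cannot be told from the documents, because the programming may have used the per-treatment-day value. The consequence is limited to this one descriptive statistic wherever it is printed. No conclusion about tolerability is affected.

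**What to change.** Reconcile the IMRT line in SAP Section 13 with protocol Table 9, so that the denominator is the planned dose intensity the SAP's sentence calls for: protocol total Gy divided by planned number of treatment days. This corrects an analysis constant and says nothing about the radiotherapy prescription.

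Section 7.1 specifies "an analysis using the primary analysis DBL date of 20-SEP-2024 for a synoptic CSR", and SAP version 2.0 is dated 14 March 2025, 175 days after that date. Tables may therefore already exist. Check the IMRT relative dose intensity row, and any listing that prints the value, and correct them if the constant 70 was used.

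The cost is one line of text, one program constant and a check of one row. Because version 2.0 is approved, the text change needs either a further SAP version or a documented correction in the programming specification and the study report.
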